7.5. Criteria for Subject Study Discontinuation

A subject may elect to discontinue from the study at any time for safety or personal reasons. All subjects who discontinue from the study should complete the early termination procedures.

Any subject with a new positive response on questions 4 and/or 5 of the Columbia Suicide Severity Rating Scale (C-SSRS) will be immediately discontinued and evaluated for risk.

Any subject with a CDRS-R or PHQ-9 assessment indicative of the onset of a new depressive episode at any visit can be discontinued from study participation at the discretion of the

Protocol EBS-101-TD-301 Version 9.0, 05 March 2024

Investigator. The Investigator will perform suicide risk assessment in subjects who respond positively to PHQ-9 question 9.

Subjects will be discontinued due to attempted suicide or suicidal behavior, oculogyric crisis, neuroleptic malignant syndrome, new onset seizures, serotonergic syndrome, or tardive dyskinesia. Subjects will also be discontinued if there are any adverse events that are Grade 4 (life-threatening consequences; urgent intervention indicated) in severity per CTCAE version 5.

Subjects who discontinue early from the study will be evaluated for one of these primary reasons: AE(s), lost to follow-up, subject choice, inadequate therapeutic effect, loss of efficacy, and administrative/other. In addition to the primary reason, the subject may have indicated one or more of these reasons as secondary reasons for discontinuation. Study disposition information will be collected on the CRF.

Subjects who discontinue treatment for any reason, other than an SAE (even if the SAE is not treatment related) or an AE (unless the AE can be determined to be unrelated to treatment), may be replaced only after consultation with Sponsor or its designee

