Randomization into the double-blind R/WD period may be closed in anticipation of reaching the target number of Relapse events. Subjects still in the open-label Stabilization period at that point may continue in the study until the Week 12 visit and upon completion of that visit subjects will have the opportunity to enter into the long-term open-label study, EBS-101-TD-391. The Sponsor may elect to re-open randomization as required.

Once the target number of Relapse events is met, all subjects may enter the long-term open-label study EBS-101-TD-391 once the Week 24/Relapse/ET visit and the Day 7 and 14 follow-up visits have been completed.

The study will be considered completed once all subjects have completed the 30-Day telephone Follow Up call or entered the open-label study EBS-101-TD-391.

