#### Intercurrent events:

The intercurrent events of initiation of additional medications to treat symptoms of TD and requirement of hospitalization for worsening symptoms of TD are included in the definition of Relapse and are considered a Relapse. The intercurrent event of loss to follow-up will be assumed unrelated to treatment and treated in estimation as censored observations. The intercurrent event of death will be handled as follows: if judged unrelated to blinded treatment or TD, death will be treated in estimation as a censored observation; if death is judged as related to blinded treatment or TD then it will be considered a Relapse. Judgement on whether a death is related to blinded treatment will be made prior to data unblinding. Data from subjects who complete or discontinue from the double-blind R/WD period without Relapse will be considered as censored observations.

Population-level summary: The time from Randomization to Relapse between the ecopipam and placebo treatment groups will be tested using a log rank test in the mITT population after having applied the treatment policy strategy specified above.

The primary efficacy analysis approach is in line with the primary estimand. Potential confounders will be identified and sensitivity and/or supplementary analysis may be used to deal with missing data and assess the robustness of conclusions.

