### 10.1.1. Sensitivity Analysis

To assess the robustness of the primary efficacy analysis, the following sensitivity analysis will be performed for the mITT and the ITT set:

Assume subjects who are lost to follow up or who discontinue the study for reasons other than Relapse or lack of efficacy meet the Relapse criteria. Their last non-missing date on study will be used as the date of Relapse. Relapse rate will be estimated using Kaplan-Meier methods and the difference between treatment arms will be tested using the log rank test. Cox proportional hazard model will be run with treatment as factor.

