#### Statistical analysis:

An exploratory analysis will be performed on all randomized subjects in R/WD period to find time from randomization to study or treatment discontinuation. The analysis method will be similar to the primary efficacy analysis as described in Section 10.1. Data from subjects who complete the study will be considered as censored observations. The log rank test will be the primary test of statistical significance. Kaplan-Meier curves will be used to compare the times to treatment discontinuation between the treatment groups. The hazard ratio and its 95% confidence interval (CI) will be estimated from the Cox proportional hazard model with treatment as a factor. All observed endpoint data will be used in this analysis, without imputation.

10.2.22. Time from Randomization (Week 12) to loss of ≥ 100% of the improvement experienced on the YGTSS-TTS from Baseline (Day 1) to the last visit (Week 12) in the open-label Stabilization period for ecopipam compared to placebo.

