where  $\Phi(.)$  denotes the cumulative distribution function of the standard normal distribution, and  $z_{\alpha/2}$  denotes the  $1-\alpha/2$  quantile of the standard normal distribution, and  $Z_{int}$  is z-value at interim analysis, which can be obtained from the output of PROC LIFETEST in SAS. The  $Z_{int}$  can be derived from the reported Logrank statistics and the corresponding covariance matrix

Derivation:

$$Z_{int} = \frac{O - E}{\sqrt{V}} = \frac{\sum_{j} (O_j - E_j)}{\sqrt{\sum_{j} V_j}}$$

where,

 $O_i = d_{1i}$ , Number of subjects in Ecopipam who developed Relapse, at distinct time j

This document is confidential.

SAP text Version: SAP text 3.0 6-Dec-2023

Controlled Document ID: 3903A.02, Effective Date 31-Aug-2020

$$E_j = \left(\frac{Y_{1j}}{Y_j}\right) * d_j, \qquad d_j = d_{0j} + d_{1j}, \text{ total number of Relapses at time j, } Y_{1j} = \text{Number of subjects in Ecopipam at time } j,$$

 $Y_i$  = Number of subjects at risk at time j.

$$V_j = \frac{Y_{0j}Y_{1j}d_j(Y_j-d_j)}{Y_i^2(Y_j-1)}, Y_{0j} = \text{number of subjects at risk at time j at control arm,}$$

 $d_i = d_{0j} + d_{1j}$  total number of Relapses at both control arm and Ecopipam at time j.

Based on the results of the above conditional power and the promising zone approach [8], the DSMB may make the following interim decisions:

- If p-value based on Logrank test at interim analysis is less than 0.005 and other measures (e.g., hazard ratio) imply a benefit of ecopipam over placebo, it is recommended to stop the study for overwhelming efficacy.
- 2) If 50%<CP<85%, then increase the number of required events such that CP based on the adjusted events ≥85% or reach the maximum number of Relapse events allowed, defined as two times the planned Relapse events (49 x 2 = 98).
- 3) If condition power (CP)<20%, it is recommended to stop the study for futility.
- 4) If all other cases, continue this study as planned.

No adjustment of the final alpha level will be required, other than the alpha spending of the IA, based on the CP approach.

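### The only sensitivity analysis specified for the primary endpoint makes no exception for administrative exits, so subjects released early at study closure could be counted as Relapses

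*SAP*

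**What the plan says.** **The rule.** SAP 10.1.1 states that "the following sensitivity analysis will be performed for the mITT and the ITT set". It then describes one analysis: subjects lost to follow-up, and those "who discontinue the study for reasons other than Relapse or lack of efficacy meet the Relapse criteria", are treated as having relapsed. On timing it says: "Their last non-missing date on study will be used as the date of Relapse". The log-rank test and Cox model are then run as for the primary analysis.

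**The primary analysis.** SAP 10.1 censors anyone who completes or leaves the R/WD period without Relapse. The ITT and per-protocol runs change the population, not the handling of exits.

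**Other sensitivity analyses.** For the primary endpoint the estimand text (SAP 7.1) offers only that "sensitivity and/or supplementary analysis may be used to deal with missing data". The imputation and tipping-point methods in SAP 10.2.25 are for mean-change endpoints.

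**Routes out of the R/WD period that are unrelated to tics.** SAP 4.1, matching Protocol 7.1, says: "Once the target number of Relapse events is met, all subjects may enter the long-term open-label study", after the Week 24/Relapse/ET visit and the two clinic follow-ups. Under SAP 13, if the interim log-rank p-value is below 0.005 in favour of ecopipam, "it is recommended to stop the study for overwhelming efficacy". Protocol 7.6 lets the sponsor end the study, or part of it, at any time. The recorded reasons for discontinuation in Protocol 7.5 end with "inadequate therapeutic effect, loss of efficacy, and administrative/other".

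**A related endpoint.** For time to treatment discontinuation, SAP 10.2.21 says: "Data from subjects who complete the study will be considered as censored observations". It names no other ground for censoring.

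**The concern.** Counting dropouts as Relapses is a reasonable stress test when leaving might reflect poor tic control or poor tolerability. An exit caused by the trial reaching its event target, or by a sponsor decision, carries no such information. In an event-driven trial it is ordinarily censored at the cut-off, as the primary analysis here would do.

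Read literally, SAP 10.1.1 reverses that. It adds the same closure hazard to both arms and so pulls the hazard ratio towards 1. If ecopipam works, more ecopipam subjects should still be at risk at any cut-off, so more of the added events are expected there. The robustness check would then depend partly on how quickly subjects were randomized and when the trial closed, and a sound primary result could look fragile for that reason alone.

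**Working it through.** **1. Reproduce the design (SAP 4.3).** Inputs: hazard ratio 0.4, two-sided alpha 0.05, power 85%, Relapse 65% on placebo and 34% on ecopipam, 1:1 allocation.

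- Freedman: events = (1.960 + 1.036)² × (1.4/0.6)² = 8.98 × 5.44 = 48.9, so 49. This matches the plan.
- Subjects: 49 / ((0.65 + 0.34)/2) = 49/0.495 = 99, against the stated 98.
- Expected Relapses from 98 subjects all followed for 12 weeks: 98 × 0.495 = 48.5. With no more than 98 randomized, the target is therefore met only when nearly everyone has finished, or not at all.

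**2. Who is still at risk at a cut-off?** Assume constant hazards over 12 weeks.

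- Placebo: −ln(0.35)/12 = 0.0875 per week. Ecopipam: −ln(0.66)/12 = 0.0346 per week. Ratio 0.396.
- Under steady entry, the average fraction still at risk among those randomized in the last 12 weeks is (1 − exp(−12λ))/(12λ). This is 0.65/1.050 = 0.619 on placebo and 0.34/0.416 = 0.818 on ecopipam.
- Expected ecopipam share of closure exits: 0.818/(0.818 + 0.619) = 57%.
- Example at 98 per 52 weeks, randomization still open: 98 × 12/52 = 22.6 recent subjects, 11.3 per arm. Still at risk: 11.3 × 0.818 = 9.2 on ecopipam and 11.3 × 0.619 = 7.0 on placebo.

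**3. Effect on the sensitivity analysis.** The documents give neither a randomization rate nor a dropout rate, so both are assumed. The simulation (600 trials per row) releases every ongoing subject at the stated event count and tests with the log-rank at two-sided 0.05. With no other dropout, the whole change is due to closure exits. The hazard ratios are medians.

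| Scenario | Closure exits, ecopipam / placebo | HR, exits censored | HR, as written | Chance of p<0.05, censored to as written | Trials with more ecopipam exits |
|---|---|---|---|---|---|
| At most 98 over 52 weeks, 49 events | 3.1 / 2.1 | 0.389 | 0.413 | 89% to 86% | 38% |
| At most 110 over 52 weeks, 49 events | 8.2 / 5.9 | 0.402 | 0.495 | 88% to 80% | 73% |
| At most 120 over 52 weeks, 49 events | 10.9 / 7.9 | 0.392 | 0.522 | 90% to 78% | 84% |
| Open at 98 per 78 weeks, 49 events | 6.3 / 4.5 | 0.401 | 0.475 | 89% to 85% | 76% |
| Open at 98 per 26 weeks, 49 events | 18.7 / 14.0 | 0.391 | 0.581 | 89% to 72% | 91% |
| Open at 98 per 52 weeks, stop at 34 events | 9.3 / 6.8 | 0.399 | 0.551 | 77% to 58% | 79% |

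The 34-event row averages over all simulated trials, not only those that would cross the 0.005 boundary.

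**4. With 5% ordinary dropout and entry over 30-52 weeks.** Here the starting value is SAP 10.1.1 with closure exits censored and ordinary dropouts counted as Relapse.

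- 98 randomized, 49 events: about 2-4 ecopipam and 2 placebo closure exits. HR about 0.43 to 0.46; chance of p<0.05 from 83-85% to 79-81%. The target is reached in about 42% of trials, and ecopipam has more closure exits in about 30%.
- 110-130 randomized, 49 events: HR about 0.42 to 0.49-0.61.
- Stop at 34 events: HR about 0.42 to 0.55-0.62.

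**5. Separating the intended penalty from the unintended one.** With 10% dropout and open randomization at 98 per 52 weeks, the median HR is 0.41 in the primary analysis. It is 0.46 when only ordinary dropouts count as Relapse, and 0.55 as written. The first step is the stress test the SAP wants; the second is the closure artefact.

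**The case against.** **Early release is inferred.** No sentence says that ongoing R/WD subjects are withdrawn at the 49th event. The text closes randomization in anticipation of the target, and the only subjects whose path it then describes are those still in open label. Subjects may enter the extension; they are not required to. The Week 24/Relapse/ET visit is simply the name of Visit 13. SAP 2.2 places the main analysis after all subjects finish or terminate early, with no data cut at event 49, and SAP 13 lets the DSMB only recommend a stop. All of this stands. Against it, completers and relapsers were already eligible for the extension, so the sentence about all subjects most naturally adds those still in the period.

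**Classification is open.** SAP 4.1 treats entry to the extension as one route to the study being complete, so a rollover might be a completer and stay censored. This also stands, although that sentence is about the study, not the subject. The disposition table in SAP 9.1 offers only completion or premature discontinuation with a reason.

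**The eCRF may already have a code.** SAP 10.2.2 cites pregnancy as a reason captured there, and Protocol 7.5 does not list it. The eCRF list may therefore be longer, so the disposition request must be conditional.

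**Consequences are limited.** The bias is towards no difference, so it does not inflate type I error. The analysis does not gate the testing hierarchy, and SAP 10.2.21 is exploratory and outside it. Closure exits could be identified from the disposition listing and explained. These points limit the size of the problem. They do not supply the missing exception.

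**Conclusion.** The gap in the text is real. The one sensitivity analysis specified for the primary endpoint counts every study discontinuation other than Relapse or lack of efficacy as Relapse, with no carve-out for administrative exits. If subjects leave at closure and are recorded as discontinuations, the rule as written gives them a Relapse they did not have.

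The size depends on assumptions the documents do not settle. It is small near the planned 98 randomized. It is material if randomization overshoots, which is possible because enrollment stops only around the time of the 49th event and randomization may be re-opened, or if the trial stops at 34 events. It is nil if everyone ongoing completes Week 24. All the figures take every ongoing subject as leaving, so they are upper bounds on the closure effect within each scenario. They also assume constant hazards, continuous detection of Relapse and the assumed entry and dropout rates.

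A reader might infer that closure subjects will become Relapses, that more of them will be on ecopipam, and that the trial's conclusion is therefore at risk. The documents do not support this. Early release and its classification are not stated, the imbalance is an expectation that fails in many simulated trials at 98 subjects, and the primary test censors these exits. What is at stake is the interpretability of the robustness check.

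**What to change.** Before unblinding, add to SAP 10.1.1: *Subjects who leave the R/WD period because the target number of Relapse events was reached, the study was stopped at the interim analysis, or the sponsor closed the study or site remain censored at their last assessment.*

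Apply the same rule in SAP 10.2.21. Make sure the disposition data identify study closure separately from the administrative/other category, if the eCRF does not already do so.

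The cost is one sentence in each of two SAP sections and at most one disposition code. It needs no extra patients or assessments and leaves the primary test as it is. Settling this in advance also avoids a reclassification that would look post hoc.

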### 10.2. Secondary and Exploratory Efficacy Endpoints and Analyses

All secondary and exploratory efficacy endpoints will be analyzed in the mITT population and ITT population according to randomized treatment. A hierarchical (fixed-sequence) testing approach will be

This document is confidential.

SAP text Version: SAP text 3.0 6-Dec-2023

Controlled Document ID: 3903A.02, Effective Date 31-Aug-2020

used for the analysis of the selected efficacy endpoints to maintain the experiment-wise type I error rate of 5%. If an endpoint is not statistically significant, confirmatory hypothesis testing will not be carried out on the remaining hypotheses, and remaining hypotheses testing will be considered exploratory rather than confirmatory.

The order of testing following the primary efficacy endpoint is outlined below:

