13.4. Planned Analysis

13.4.1. Efficacy Analysis

The primary efficacy endpoint is time from Randomization to Relapse defined as a loss of $\geq 50\%$ of the improvement experienced on the YGTSS-TTS at the last visit in the open-label Stabilization period (Week 12), or initiation of additional medications to treat symptoms of TD, or requirement of hospitalization for w rsening symptoms of TD in subjects ≥ 6 and < 18 years during the double-blind R/WD period for ecopipam compared to placebo. Data from subjects who complete or discontinue from the double-blind R/WD period without Relapse will be considered as censored obs rvations. The log rank test will be the primary test of statistical significance. Kaplan-Meier curves will be used to compare the times to relapse between the treatment groups. The hazard ratio and its 95% confidence interval (CI) will be estimated from the Cox proportional hazard model with treatment as a factor. The proportional hazards assumption will be evaluated graphically and analytically, for example by assessing martingale and Schoenfeld residuals and by modeling time-dependent covariates. The analysis of the primary efficacy endpoint will be performed in the mITT and PP populations according to the randomized treatment. Details will be provided in the Statistical Analysis Plan.

The time-to-event secondary and exploratory endpoints related to Relapse will be analyzed in a similar manner as the primary endpoint. The exploratory endpoints of mean change will be assessed with a Mixed Model for Repeated Measures (MMRM) model using the SAS MIXED procedure, with a REPEATED statement, with no imputation. The model will include fixed effects for treatment, visit, the interaction between treatment and visit, and a covariate for baseline score for the given assessment and other covariates such as gender, age group, race/ethnicity, and region. All secondary and exploratory endpoints will be analyzed in the mITT population according to randomized treatment. Details will be provided in the Statistical Analysis Plan.

Protocol EBS-101-TD-301 Version 9.0, 05 March 2024

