For exploratory endpoints of mean change, the difference in means between treatment arms in change from Randomization (Week 12) to Week 24 or from Baseline (Day 1) to Week 24, a sensitivity analysis may be performed. For the intercurrent events of study treatment discontinuation due to lack of efficacy, treatment related adverse events, death prior to Week 24 and Relapse for subjects with no assessment at Week 24, the non-collected data of assessment at Week 24 will be multiple imput d using similar subjects (relevant demographic/baseline characteristics) from the placebo arm. For exploratory endpoints of mean change to fixed time point, additional analyses will be performed by time point.

In consideration of missing data, additional multiple imputation or tipping point methods may be used as a sensitivity analysis, such as:

- Missing at Random (MAR) predictive mean matching multiple imputation method
- Missing not at Random (MNAR) "jump to reference" multiple imputation method
- Tipping point analysis under MNAR assumption
- The mean change from Baseline (Day 1) to Week 12 (open-label) in YGTSS-TTS will be calculated. The paired t-test will be used for analyzing the change from baseline within treatment.
- The percentage of subjects with a 25% or greater decrease in their YGTSS-TS will be analyzed using Fisher Exact test.
- A fixed-sequence statistical strategy will be used to test selected efficacy endpoints in a predefined rank order hierarchy which will be outlined in the SAP.

Protocol EBS-101-TD-301 Version 9.0, 05 March 2024

The full details will be specified in the SAP.

Subgroup analyses will be conducted on all efficacy endpoints for the following populations:

- Children (≥ 6 and < 12 years of age), Adolescents (≥ 12 and < 18 years of age), and Adults (≥ 18 years of age).
- Subjects per region
- Males and Females
- Ethnicity and Race

Additionally, Time from Randomization to a loss of \geq 50% improvement on the YGTSS-TTS will also be analyzed using the following subgroups:

• Early Responders (at Week 4) and Later Responders (at Week 8)

The treatment of missing data and sensitivity analyses for the endpoints will be specified in the Statistical Analysis Plan.

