# 4. Study Details/Design

### 4.1. Brief Description

This is a multicenter study which includes an open-label period followed by double-blind, placebo-controlled, randomized withdrawal period in children (≥ 6 and < 12 years of age), adolescents (≥ 12 and < 18 years of age), and adult subjects (≥ 18 years of age) with TD.

After providing informed consent (adult subjects or caregivers for children/adolescents) and assent (children/adolescents) and following an up to 28-day Screening period, and with agreement by Eligibility Review by the study team, subjects will proceed to the Baseline visit (Day 1).

At the Baseline visit, eligible subjects will be entered into an open-label Stabilization period and start a 4-week Titration phase to achieve a target steady-state dose of 1.8 mg/kg/day ecopipam (2mg/kg/day ecopipam HCl) followed by an 8-week open-label Maintenance phase.

During the open-label Stabilization period, subjects will return to the clinic at Baseline (Day 1) and Weeks 4, 8 and 12. Subjects will have a telephone visit at Week 2 to assess adverse events (AEs) and other safety parameters. Efficacy assessments will be conducted at Weeks 4, 8 and 12. PK samples will be collected at Weeks 4 and 8. A PK assessment may be collected at Week 12 if the Week 8 PK assessment is missed. Safety assessments will be conducted at all visits.

Responders to ecopipam, defined as those with ≥ 25% improvement from Baseline on the Yale Global Tic Severity Scale-Total Tic Score (YGTSS-TTS) at both Weeks 8 & 12 during the open-label Stabilization period, will be randomized to ecopipam 1.8 mg/kg/day (2 mg/kg/day ecopipam HCl) or placebo in a 1:1 fashion and enter a double-blind Randomized-Withdrawal (R/WD) period at Week 12. Subjects randomized to placebo will be tapered off ecopipam in a blinded fashion in decrements of 22.4-mg/day (25-mg/day ecopipam HCl).

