# 6.3. Modified Intent-to-Treat (Primary Efficacy Analysis Set)

The Modified Intention-to-Treat (mITT) set will include all randomized subjects who received at least one dose of study drug post randomization. The mITT set will be used for the analysis of primary, secondary and exploratory efficacy endpoints. Subjects will be analyzed according to randomized treatment.

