#### Statistical analysis:

The mean change from Baseline (Day 1) to Week 12 (Week 4, 8 and 12 open-label) in YGTSS-TTS will be calculated. The paired t-test will be used for analyzing the change from baseline. All observed endpoint data will be used in this analysis, without imputation.

Summary statistics will be presented along with a full data listing.

10.2.14. Percentage of subjects with a decrease in their YGTSS-TTS by 25% or greater at any time point from Baseline (Day 1) to Week 12.

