#### Statistical analysis:

The percent of subjects with a 25% or greater improvement on the YGTSS-TTS score at any time between the Baseline visit to the Week 12 visit (Week 4, 8 and 12) will be considered as a Response. Any subject who has at least 1 Response (>=25% improvement) will be considered as a Responder; otherwise, the subject will be considered a Non-Responder.

Summary statistics for visit week 4, week 8, week 12 and overall will be presented along with a full data listing.

In addition, the percent of subjects who have maintained Responder status from the previous visit (i.e., responder at Week 4 and still a responder at Week 8) will be presented.

Similar analyses will be performed for 50%, 75%, and 100% improvement.

10.2.15. Mean change from Baseline (Day 1) to Week 24 in the YGTSS-TTS for ecopipam compared to placebo.

See section 10.1 for a description of the YGTSS-TTS. An exploratory analysis will be performed on the change in YGTSS-TTS from Baseline to Week 24 (Weeks 4, 8, 12, 13, 14, 15, 16, 18, 20, 22 and 24).

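### Exploratory endpoints 12 and 13 describe the open-label period but are assigned to randomized subjects only, so the any-time responder rate is 100% by construction and the mean Week 12 change is inflated by selection

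*SAP*

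**What the plan says.** The analysis set is fixed by blanket sentences. SAP 10.2: "All secondary and exploratory efficacy endpoints will be analyzed in the mITT population and ITT population according to randomized treatment". SAP 6.3: "The mITT set will be used for the analysis of primary, secondary and exploratory efficacy endpoints". Protocol 13.4.1: "All secondary and exploratory endpoints will be analyzed in the mITT population according to randomized treatment". Protocol 13.1 gives the same rule and adds that every mITT analysis is repeated in ITT.

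Both sets require randomization. The mITT set "will include all randomized subjects who received at least one dose of study drug post randomization", and ITT is everyone randomized (SAP 6.4). The gate is in SAP 4.1 and Protocol 7.1: subjects whose YGTSS-TTS improves by 25% or more "at both Weeks 8 & 12 during the open-label Stabilization period, will be randomized".

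Two exploratory endpoints end at Week 12, before the double-blind period:

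- Endpoint 12 (SAP 10.2.13), mean YGTSS-TTS change: "The paired t-test will be used for analyzing the change from baseline", on observed data without imputation.
- Endpoint 13 (SAP 10.2.14), response at Week 4, 8 or 12: "Any subject who has at least 1 Response (>=25% improvement) will be considered as a Responder". Everyone else is a Non-Responder. Rates are given for each visit and overall, with the share who keep responder status from the previous visit, and are repeated at thresholds of 50%, 75% and 100%.

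Neither section names an analysis set. The protocol adds a test that the SAP does not carry: "The percentage of subjects with a 25% or greater decrease in their YGTSS-TS will be analyzed using Fisher Exact test".

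**The concern.** The step that selects subjects for randomization uses the same score, at the same visits, as the two endpoints. Restricting those endpoints to randomized subjects removes everyone who failed to respond at Week 8 or Week 12, and then asks how many responded and by how much. The first answer is fixed in advance and the second is biased upwards.

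These are the only listed efficacy endpoints confined to the open-label period. On the assigned sets they cannot describe how treated patients responded, and a reader of the report could take the selected figures for the response in everyone treated. If the set is left open, the choice between about 98 and about 196 children and adolescents as denominator could be made after the open-label data are known.

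**Working it through.** **The plan's own figures.** Inputs from SAP 4.3: hazard ratio 0.4, two-sided alpha 0.05, power 85%, Relapse proportions 65% and 34%, open-label response rate 50%.

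- Events (Freedman): (1.960 + 1.036)² × (1.4/0.6)² = 8.98 × 5.44 = 48.9, so 49. This matches.
- Events from 49 per group: 49 × (0.65 + 0.34) = 48.5. This matches.
- Enrolment: 98 / 0.50 = 196. This matches.

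On these assumptions 196 - 98 = 98 treated children and adolescents fall outside ITT and mITT. The plan states no response rate for the roughly 40 adults.

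**Responder rate.** This is set logic and needs no data. Let R4, R8 and R12 be an improvement of at least 25% at each visit. Membership of ITT or mITT requires R8 and R12.

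| Quantity in SAP 10.2.14 (25% threshold) | Value in ITT/mITT |
|---|---|
| Week 8 rate, Week 12 rate | 100% |
| Any-time rate, P(R4 or R8 or R12, given R8 and R12) | 100% |
| Maintained, Week 8 to 12 | 100% |
| Non-Responder category | empty |
| Week 4 rate | not fixed |
| Maintained, Week 4 to 8 | 100% among Week 4 responders; equals the Week 4 rate if all subjects are the denominator (the SAP does not say which) |

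Only a subject randomized in error could lower the 100% figures.

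**Mean Week 12 change.** The direction follows from selection on the outcome. The size has to be illustrated, because the documents do not give all the inputs.

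- From the documents: Phase 2b ecopipam mean change -9.87 (Protocol Table 2); difference 3.4 and effect size 0.48, so SD about 3.4/0.48 = 7.1; a 30% average reduction, so baseline about 9.87/0.30 = 32.9 (Protocol 5.3.2).
- Assumed: bivariate normal changes at Weeks 8 and 12 with equal means, SD 6 to 8.5, correlation 0.6 to 0.8, mean baseline 31 to 33. Subjects are kept if both changes reach 25% of baseline.

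| Mean baseline | Mean Week 12 change, selected | Ratio to -9.87 |
|---|---|---|
| 31 | -13.8 to -16.1 | 1.40 to 1.63 |
| 32.9 | -14.1 to -16.4 | 1.43 to 1.66 |

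The overstatement is therefore about 40% to 65%. Widening the correlation to 0.5 to 0.85 with baseline held at 32.9 gives -14.2 to -16.6 (44% to 68%). In that wider run 41% to 52% of subjects pass both visits, close to the planned 50%, so the inputs are not implausible.

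**What is inflated but not fixed.** In the same wider run, with an assumed Week 4 mean of -6, the Week 4 rate in selected subjects is about 55% to 72%. The share with a 50% improvement at Week 12 is 26% to 45% in selected subjects, against 14% to 22% in all treated. The any-time 25% rate in all treated subjects is 67% to 79%, an informative figure where the assigned set gives 100%.

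**The case against.** The strongest reply is that all open-label subjects were plainly meant. SAP 10.2.13 and 10.2.14 omit the by-treatment-group phrase that the between-arm summary sections carry. SAP 10.2.14 defines a Non-Responder category that would be empty in mITT. Analysis by randomized treatment does not fit a period in which everyone takes ecopipam. These are real hints, and they are why a firm prediction that the report will show 100% goes too far. They do not override a sentence that covers all exploratory endpoints, is repeated across both documents, and meets no exception. If all treated subjects were intended, the text contradicts that intent and needs the same edit.

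Several stronger readings that a reader might infer are not supported:

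- *The 50% response assumption cannot be checked.* SAP 9.1 reports the Safety Set, open-label discontinuations and the number randomized, which allows a crude check, subject to any closure of randomization. Endpoint 13 measures any-time response, not response at both visits, so it would not check the 50% directly on any set.
- *The set is what makes the paired t-test positive.* With the Phase 2b placebo mean of -6.42, SD 7.1 and all 236 treated subjects, t = 6.42 / (7.1/√236), about 14. An uncontrolled pre-post test is strongly positive on any set.
- *The Safety Set is barred from efficacy use.* SAP 6.2 assigns it to safety endpoints but does not say only those, and SAP 9 already uses it for demographics, medical history and medication.
- *A Fisher test of 100% against 100% is planned in the SAP.* It appears only in Protocol 13.4.1.

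**Conclusion.** The point holds. As written, endpoints 12 and 13 are analysed only in subjects who have already met the response criterion. The any-time, Week 8 and Week 12 responder rates and the Week 8-to-12 maintained rate are 100% by construction, barring randomization errors. The Week 4 rate and the 50%, 75% and 100% thresholds are affected by selection but not fixed at 100%.

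The mean Week 12 change is certainly biased towards greater improvement. The figure of about 40% to 65% is an illustration that rests on the Phase 2b mean and on assumed SD, baseline, correlation and normality.

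A reader might infer that this threatens the trial's main conclusion. It does not: both endpoints are exploratory and outside the fixed testing sequence, so the primary and secondary analyses and type I error are unaffected. It should be corrected because two stated endpoints cannot describe what they are meant to describe.

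**What to change.** 1. Exempt endpoints 12 and 13 from the blanket mITT/ITT sentences in SAP 10.2 and 6.3 and in Protocol 13.1 and 13.4.1. Changing only the endpoint sections would leave the contradiction in place.
2. State in SAP 10.2.13 and 10.2.14 that both are analysed in all subjects who took at least one open-label dose (the existing Safety Set), overall and by age group, with estimates and 95% confidence intervals.
3. For endpoint 13, count subjects with no qualifying score as non-responders. For endpoint 12, keep observed cases without imputation, as SAP 10.2.13 already provides, and report the number contributing at each visit.
4. Remove the Fisher test from Protocol 13.4.1. The open-label period has no comparator, and the SAP already omits the test.

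The cost is a few sentences in each document and two sets of tables on a population already defined. The downside for the sponsor is that the reported open-label figures become less favourable.
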